8.1 Sub-analyses

8.1.1 Sub-analysis 1: Comparison of PFA VS RFA

This sub-analysis will compare the 12-month efficacy and safety of PFA and RFA using data collected in the main study.

All analyses will be performed post-hoc within the predefined data framework of the primary trial; no additional interventions, visits, or consent are required.

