2.3 Thermocool Smarttouch® & Thermocool Smarttouch® SF (ST&STSF) Catheter

ST catheter is an irrigated-tip ablation, contact-force (CF)-sensing catheter indicated for cardiac mapping and ablation. The catheter contains a porous tip with 6 holes at the distal end. STSF catheter is a newer generation of the CF-sensing and irrigated-tip ablation catheter indicated for cardiac mapping and ablation. The catheter contains a porous tip with 56 holes at the distal end. The increased number of holes at the distal tip improves the cooling effect at the catheter-tissue interface. This newer design also requires less fluid delivery through the distal tip which could reduce the risk of volume overload. When used in conjunction with the Carto®3 system, the catheter of both kinds is able to provide real-time CF data during catheter ablation. Due to the product's indication restrictions, we suggest to use ST/STSF catheter for persistent AF patients.

SURPOINT is another new software module running with Carto 3 system. When used with ST and STSF catheter, SURPOINT is able to display AI value real-time on the Carto 3 system. The AI values can be used to guide the catheter ablation for durable lesion creation by ST and STSF catheter.

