2.5 Varipulse Platform

The VaripulseTM platform from Biosense Webster is an innovative pulsed field ablation (PFA) system designed for treating atrial fibrillation. It uses a 7.5Fr circular catheter with 10 electrodes, each with its own irrigation pore to

improve cooling during ablation. The catheter is highly flexible, with 180° deflection in one direction and 90° in the other, making it easier to reach all pulmonary veins, including the more difficult-to-access right inferior pulmonary vein (RIPV).

The PFA energy is delivered in a bipolar pattern between alternating electrodes (e.g., between electrodes 1 and 3), as well as between adjacent pairs (e.g., electrodes 1–2 and 2–3). The system applies 1800V of pulsed energy through brief microsecond-long pulses, lasting a total of 250 microseconds per application.

During the procedure, irrigation is maintained at a flow rate both at rest and during ablation, to ensure safe and effective procedure.

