3 THE TRIAL

3.1 Trial design

This is a non-Inferior, Multi-Center, Prospective Randomized Controlled Trial ((1:1 randomization) conducted in China. The study aims to consecutively enroll up to 724 procedures over the course of one year at 10 EP centers with non-fluoroscopic labs accredited by the Chinese Heart Rhythm Society. The anticipated total study duration is 36 months, with a follow-up period of 12 months for each participant. The study will be completed after the last enrolled subject has finished the 12-month follow-up period.

Following informed consent, obtained either during the pre-procedure office visit or during hospitalization for the procedure, baseline data will be collected. This data will include patient demographics, medical history, prior treatments, and laboratory test results.

The initial enrollment ratio between PFA and RF was projected to be evenly distributed at 50% each. Peri-procedural data, including procedural details, ablation strategies, acute success rates, VISITAG parameters, and any complications or adverse events, will be recorded up to the patient's discharge.

Post-discharge, participants will undergo follow-up evaluations at 1,2, 3,6,9,12 months after the procedure. The follow-up schedule will remain unchanged even if a repeat ablation procedure is required.

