3.4.2 Secondary endpoints

[figure not shown]
- The acute success of the procedure.
- The proportion of intraoperative conversion to using X-ray.
- Utilization of lead personal protective equipment (PPE) and wear time.Well-being survey of staff.
- The proportion of patients with recurrence of targeted arrhythmia during the first 90 days post-ablation.
- Early recurrence of atrial arrhythmias, defined as any AF/AFL/AT episode lasting >30 seconds occurring during the blanking period.
- Late recurrence of atrial arrhythmias, defined as any documented AF/AFL/AT episode lasting >30 seconds occurring after the blanking period and up to 12 months.
- Impact of early recurrence on late recurrence, assessed through survival analysis and multivariable adjustment to evaluate whether early recurrence predicts subsequent late recurrence.
- AF burden, assessed by scheduled rhythm monitoring (e.g., 7-day Holter at 3, 6, 9, and 12 months), expressed as the proportion of time spent in AF during the monitoring period.
- Incidence of peri-procedural complication.
- Total procedure duration, ablation time.
- changes in quality-of-life (using the AF Effect on Quality of Life (AFQT) and the EuroQol Health-Related Quality-of-Life 3-Level (EQ-5D-3L)).

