3.5 Sample Size

For **efficacy** as the primary endpoint, sample-size was calculated by non-inferiority log-rank test with 1:1 design. The expected recurrence rate of AF is 30% for control group based on previous studies and our experience, and a hazard ratio of 1.3 was used for establish non-inferiority. Based on a power of 80% and an alpha of 0.05, proportion lost to follow up 5%, a sample size of **724 patients (362 for each group)** was estimated.

Safety endpoints will still be collected in detail and analyzed for comparison between the groups, but they will not be used to determine the sample size.

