3.6 Study flowchart

3.7 Planned trial interventions

Ablation Procedure details (study and control group)

The study will target AF catheter ablation procedures. After obtaining written informed consent, eligible patients will be randomized in a 1:1 fashion to one of the following two groups:

Group 1: Non-Fluoroscopic Lab Group

1. Ablation procedures will utilize ICE and 3D mapping systems for non-fluoroscopic guidement. ICE is mandatory for real-time anatomical visualization.
2. No routine fluoroscopy will be used, except if deemed necessary for safety (e.g., complications or unexpected procedural difficulties), adhering to the ALARA principle.
3. Pulmonary vein isolation (PVI) will be the sole ablation strategy, following the study protocol.

Group 2: Fluoroscopic Lab Group (DSA Lab)

1. Ablation procedures will be conducted in a fluoroscopic lab. The use of ICE, 3D EP mapping systems, and other tools will follow the same recommendations as in the non-fluoroscopic lab group.
2. Radiation exposure will be closely monitored and minimized in accordance with the ALARA (As Low As Reasonably Achievable) principles when necessary.
3. Similar to Group 1, PVI will be the sole ablation strategy, as per protocol.

Ablation strategy

The primary ablation strategy for both groups will be **pulmonary vein isolation (PVI)**. Additional ablation, including but not limited to linear ablation, complex fractionated atrial electrogram (CFAE) ablation, or superior vena cava (SVC) isolation will not be allowed unless required in the presence of one the following:

- Documented atrial flutter (AFL) or atrial tachycardia (AT) observed during the procedure, or
- Arrhythmias originating from the specific region requiring intervention.

Energy Selection Principles

At the time of enrollment, the investigator will determine the planned ablation energy modality (radiofrequency [RF] or pulsed field [PF]) according to routine clinical practice, patient characteristics, procedural indications, device availability, and patient preference. The choice of energy modality is made prior to randomization, and the study protocol does not mandate or interfere with individual clinical decision-making.

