Given the increasing adoption and availability of pulsed field ablation (PFA) in current clinical practice, and in order to maintain the external validity of the study in the future era when PFA is expected to become the predominant ablation modality, the study adopts a population-level expectation for patients enrolled after the effective date of this protocol version:

Without influencing individual clinical judgment, the cumulative proportion of PFA among subsequently enrolled patients is expected to progressively increase, with a target of achieving $\geq 50\text{-}60\%$ of all newly enrolled cases.

This expectation aims to optimize the overall energy composition of the study cohort to better reflect evolving clinical practice trends. It does not impose restrictions on individual patient-level energy selection and does not apply to participants enrolled prior to the implementation of this protocol amendment.

Recommendations

- 1) The configuration of the Non-fluoroscopic Lab needs to be in accordance with the latest expert consensus recommendations (Jiang C, et al. Pacing Clin Electrophysiol. 2023 Sep;46(9):1035-1048).

- 2) The use of ICE catheter is required for both groups. The application of ICE technology includes but is not limited to: visualizing the cardiac anatomy; guiding catheter placement, transeptal puncture (if necessary); constructing the geometry; monitoring intracardiac thrombus and cardiac effusion throughout the procedure.
- 3) Magnetic mapping catheters (e.g. Lasso, PentaRay, or DECANAV) is recommended to create the cardiac geometry.
- 4) A safe, rapid, and smooth plan for transfer to the DSA lab should be established if no mobile DSA equipment is available in the Non-fluoroscopic EP Lab. In the event of an emergency requiring the use of DSA, patient transfer should be completed in a minimum period to maximize patient safety.
- 5) If deemed necessary, X-ray imaging may be utilized to guide catheter placement and monitor for potential complications. The use of X-ray must adhere to the As Low As Reasonably Achievable (ALARA) principle, ensuring radiation exposure is minimized while maintaining procedural safety and effectiveness.

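### Sub-analysis 1 compares PFA with RFA, an investigator's choice, without calling the contrast non-randomised or exploratory; with the unadjusted tests Section 8 states, its efficacy result is open to confounding

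*Protocol*

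**What the plan says.** Protocol Section 8.1.1: "This sub-analysis will compare the 12-month efficacy and safety of PFA and RFA using data collected in the main study". The section describes its analyses as post-hoc within the main trial's data. It names no test, model or covariate, and does not say that the energy groups are non-randomised.

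Section 3.7 has the investigator choose the energy before randomisation, "according to routine clinical practice, patient characteristics, procedural indications, device availability, and patient preference". Only the lab type is randomised.

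Three passages bear on how the energy groups may differ:
- Section 2.3, on the ST and STSF radiofrequency catheters: "we suggest to use ST/STSF catheter for persistent AF patients". Section 2.5 sets no AF-type limit on the pulsed field platform, described as an "innovative pulsed field ablation (PFA) system designed for treating atrial fibrillation".
- Section 3.1: "The initial enrollment ratio between PFA and RF was projected to be evenly distributed at 50% each". For patients enrolled after the amendment, Section 3.7 adds that "the cumulative proportion of PFA among subsequently enrolled patients is expected to progressively increase".
- Section 3.8.2 treats PVI as well established mainly in paroxysmal AF and its effect in persistent AF as still open.

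Section 8 gives the t-test, Mann-Whitney, Chi-square and Fisher tests, uses Kaplan-Meier descriptively, and applies P<0.05 to all tests. A log-rank test appears in Section 3.5, for sizing only ("sample-size was calculated by non-inferiority log-rank test with 1:1 design"). Adjustment is named for another question, in Section 3.4.2: "Impact of early recurrence on late recurrence, assessed through survival analysis and multivariable adjustment". Sub-analyses 2 and 3 (Sections 8.1.2 and 8.1.3) are called exploratory, and sub-analysis 3 stratifies by AF type.

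**The concern.** A comparison of two treatments that physicians chose for their patients mixes the treatment effect with the reasons for the choice. The protocol lists such reasons: patient characteristics, indication, device availability and preference. If persistent AF recurs more often after PVI and goes more often to RF, a crude comparison shows a PFA advantage that is case mix. Device availability ties energy to centre, and the rising PFA share ties it to calendar time. Either could bias the result in either direction.

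At stake is how a published PFA-versus-RFA result would be read. It would come from a randomised trial, with a P value under a blanket 5% rule, and without the exploratory label that its two companion analyses carry.

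**Working it through.** **The plan's own figure.** The protocol gives no size or power for the energy contrast. Its only figure is 724 patients for the lab comparison. This reproduces: 4 × (1.645 + 0.842)² / (ln 1.3)² gives 360 events, and 360 / 0.498 = 723. The 0.498 is the event probability for hazard 0.30, 5% loss, accrual 1 and total time 3, as in the synopsis table. Here 724 serves only as a denominator.

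**Inputs.** From the protocol: 724 patients, and a PFA target of at least 50-60% (Section 6.5). I take 55%, so 398 PFA and 326 RF patients. Assumed, because the documents give neither: recurrence by AF type, and the persistent-AF share within each energy. The true energy effect is set to zero.

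**Formula.** Crude recurrence in an energy group = paroxysmal rate + (persistent rate − paroxysmal rate) × persistent share. The chance of a two-sided P<0.05 is that of a pooled two-proportion z test.

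**Worked case.** Recurrence 25% paroxysmal and 40% persistent; persistent AF 10% of PFA and 50% of RF cases.
- PFA: 0.25 + 0.15 × 0.10 = 26.5%. RF: 0.25 + 0.15 × 0.50 = 32.5%. Pooled: 29.2%.
- Standard error: √(0.292 × 0.708 × (1/398 + 1/326)) = 0.0340.
- 0.060 / 0.0340 = 1.76, and Φ(1.76 − 1.96) = 0.42.

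| Recurrence, paroxysmal / persistent | Persistent share, PFA / RF | Crude recurrence, PFA vs RF | Chance of P<0.05 |
|---|---|---|---|
| 25% / 40% | 10% / 50% | 26.5% vs 32.5% | 42% |
| 25% / 40% | 20% / 50% | 28.0% vs 32.5% | 26% |
| 25% / 35% | 10% / 50% | 26.0% vs 30.0% | 22% |
| 25% / 35% | 20% / 50% | 27.0% vs 30.0% | 14.5% |
| 27% / 32% | 10% / 50% | 27.5% vs 29.5% | 9% |
| 27% / 32% | 20% / 50% | 28.0% vs 29.5% | 7% |
| any | equal | equal | 5% |

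**Weak channelling.** Suppose half of the persistent patients get PFA, with recurrence 25% / 40%. The chance is 5% if PFA is 50% of cases. It reaches 14% if PFA is 60% and persistent AF is 50% of patients: shares 0.25/0.60 = 41.7% and 0.25/0.40 = 62.5%, recurrence 31.3% vs 34.4%. It is 18% if persistent AF is 60% of patients.

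**Precision cost of stratifying by AF type** (worked case, variance of the log hazard ratio ≈ 1/events + 1/events).
- Crude: events 105.5 and 106.0, SE 0.138.
- Paroxysmal stratum: events 89.6 and 40.8, variance 0.0357.
- Persistent stratum: events 15.9 and 65.2, variance 0.0782.
- Combined: SE = √(1/(1/0.0357 + 1/0.0782)) = 0.157, ratio 1.14. With 20% persistent in PFA: 0.144 / 0.136 = 1.06.

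**Centre and period** (simulations of 2,000 trials each, 16 centres, no energy effect, all links assumed). Where centres differ in both PFA use and recurrence, the crude hazard ratio was 0.881. The model adjusted for AF type, calendar time, baseline covariates and randomised lab, but not centre, gave 0.878. Stratifying by centre gave 1.006. Where the hazard fell 30% over the year while PFA use rose, the crude hazard ratio was 0.951 and continuous calendar time restored it to 0.999.

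**Safety.** Section 3.8.1 expects complications of 2-3%: 0.02 × 724 = 14 and 0.03 × 724 = 22 events, too few for this adjustment.

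**The case against.** Several points on the other side stand.

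- Section 8.1.1 does say post-hoc, which tempers any confirmatory reading. But that word concerns timing, not how the groups were formed.
- Section 3.7 makes plain that energy is chosen, so a careful reader can see that the contrast is not randomised. The gap is that 8.1.1 does not say so.
- Models and covariates for a sub-analysis are commonly left to the statistical analysis plan. A reader might infer that the protocol commits this comparison to crude tests. It does not: 8.1.1 names no test, the Section 8 paragraph is generic, and part of the synopsis is missing from the text at hand. The point rests on what Section 8 states and on the missing label.
- A reader might infer that the protocol sends persistent AF to RF. Section 2.3 is a suggestion, and with another RF catheter described in Section 2.4 it can be read as a choice among RF catheters. The trial also admits only persistent AF of one year or less, so the prognostic gap may be small.
- Period is linked to energy, and centre only through device availability. Neither is linked to outcome in the documents.

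It does not follow that nothing needs changing. Sub-analyses 2 and 3 carry the exploratory label and sub-analysis 3 is stratified by AF type, while the one treatment comparison among the three has neither.

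**Conclusion.** The concern holds in this limited form. Sub-analysis 1 is a non-randomised comparison that is not labelled as one, and the tests Section 8 states would leave its efficacy result open to confounding, possibly by AF type and also by centre and calendar time.

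The size is unknown. The range from 5% to about 42% rests wholly on assumed recurrence rates and AF-type mixes, and those inputs are not bounds. A PFA advantage follows only if persistent AF both recurs more and goes more to RF. No direction can be derived for safety.

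A reader might also infer that the main result is compromised. It is not: energy is fixed before the lab is randomised, so the lab comparison is unaffected. No primary or listed secondary endpoint is a PFA-versus-RFA comparison. Priority is low to moderate.

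**What to change.** In Section 8.1.1:
- State that the PFA-RFA comparison is non-randomised and exploratory.
- In place of the crude tests, estimate the energy effect on the primary efficacy endpoint with a Cox model stratified by AF type and adjusted for calendar time of enrolment (continuous) and a short list of baseline covariates, for example age, left atrial diameter and LVEF.
- Report a centre-stratified version alongside it, since the model without centre does not remove centre differences.
- Report safety by energy descriptively, without a significance claim.

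If the statistical analysis plan already does this, a cross-reference and the label are enough.

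The cost is a few lines and no new data: AF type and the covariates are on the forms in Section 4.3, and consent is dated (Section 9). Intervals widen. Under the strong-channelling assumptions the standard error of the log hazard ratio is about 6-14% larger with AF-type stratification, and about 10-19% larger with centre strata in the simulations. Centres that use one energy only add nothing to the centre-stratified estimate. Unmeasured reasons for the energy choice remain, so the label is needed even with adjustment.

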8.1.2 Sub-analysis 2: Impact of blanking period definitions following PFA

This sub-analysis will explore the effect of different blanking period definitions (1-month, 2-month vs 3-month) on arrhythmia-free success rates after PFA, using the same dataset and follow-up schedule as the main study.

It is an exploratory analytical component of the main trial and does not involve separate randomization or data collection.

8.1.3 Sub-analysis 3: Impact of AF duration and symptom/diagnosis-to-ablation interval on ablation success

This sub-analysis will explore whether different time definitions influence the interpretation of 12-month ablation success. Two analytical models will be applied using the main trial dataset without additional interventions or visits:

- **Model A (documented AF duration model):** Patients will be stratified by AF type (paroxysmal vs. persistent ≤ 1 year) and analyzed according to documented AF duration based on the first recorded AF episode.

- **Model B (symptom/diagnosis-to-ablation interval model):** Patients will be stratified according to the interval from initial symptom onset or first AF diagnosis—whichever occurs earlier—to the ablation procedure, with categories defined by the actual distribution of the study population.

This exploratory sub-analysis compares analytical approaches only; it does not modify clinical management, affect randomization, or add data collection requirements.

9. Consenting Process

Local IRB approval must be obtained before patient enrollment. Informed consent form signed and dated by both investigator and subject must be obtained from all subjects prior to exporting the data from the hospital database for this study. Any modifications to the Patient Informed Consent Form must be approved by the Ethics Committee (EC). The copy of the Patient Informed Consent Form approved by EC, along with the copies of consent forms signed by every subject, must be maintained by every investigator in a designated clinical trial master file. A signed copy of the consent form must be given to each subject. It is the investigator's responsibility to ensure that the informed consent process is performed in accordance with good clinical practices (GCP).

10. Plans For Publication

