7.5.4 SUSARs Reporting

Suspected Unexpected Serious Adverse Reactions [SUSARs] will undergo expedited reporting to relevant regulatory authorities (e.g., research ethics committees, National Medical Products Administration, and National Health

Commission of the People's Republic of China). Investigators must report all SUSARs to sponsor as soon as possible and 24h of learning of the event. These SUSARs will be centrally reviewed and reported by the sponsor as soon as possible:

For fatal or life-threatening SUSARs, sponsor must report as soon as possible and within 7 days of learning of the events. Active follow-up must be completed within the following 8 days (The first day of learning of the event is considered 0 day).

For fatal or life-threatening SUSARs, sponsor must report as soon as possible and within 15 days of learning of the events.

8. Statistical analysis

Continuous variables are expressed as mean \pm SD if normally distributed or median (interquartile range [IQR]) if not normally distributed. Intergroup differences will be compared by student's t-test (normally distributed data with equal variance) or Mann-Whitney U test (failed either normality or equal variance test). Categorical variables will be presented as percentages and compared by using the Chi-square test or Fisher's exact test. The Kaplan-Meier method will be used to describe event-free rates over time. The statistical significance for all tests will be accepted at $P < 0.05$.

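### Sub-analysis 3, Model B analyses a continuous time interval only as sample-derived categories; this discards information, and by an amount that depends on choices the protocol does not state

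*Protocol*

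**What the plan says.** Section 8.1.3 asks whether the way time is defined changes how 12-month ablation success is interpreted. It sets out two models.

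- **Model A** stratifies by AF type (paroxysmal, or persistent up to one year) and analyses by documented AF duration. The scale for duration is not stated.
- **Model B** starts from the earlier of symptom onset and diagnosis: "Patients will be stratified according to the interval from initial symptom onset or first AF diagnosis". The groups are formed "with categories defined by the actual distribution of the study population".

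No number of groups, quantile rule, test, effect size or power is given for either model. The status is explicit: "This exploratory sub-analysis compares analytical approaches only".

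Section 8 sets the general approach: chi-square or Fisher's exact test for categorical variables, Kaplan-Meier for event-free rates, and a significance threshold of P < 0.05 ("The statistical significance for all tests will be accepted at" that level). It names neither a trend test nor a regression on a continuous covariate. Survival analysis with multivariable adjustment appears only in the secondary endpoint that relates early to late recurrence (Section 3.4.2).

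**The concern.** Once an interval is grouped, everyone in a group is treated as having the same interval, so variation within groups no longer contributes. If the groups are compared without regard to their order, k groups also use k − 1 degrees of freedom for what may be a single gradient. Cut-points taken from this sample make the resulting contrasts hard to set beside those of another cohort.

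The choice of categories is made in the protocol itself. An unseen SAP might settle how many groups there are and where the limits fall, but Section 8.1.3 has already fixed the scale.

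Two things are at stake, both within this sub-analysis. A real gradient could be missed, and a null Model B could then be read as showing that delay to ablation does not matter. Also, the sub-analysis compares time definitions. If Model A handled duration on one scale and Model B on another, a difference between them could reflect scale and not definition.

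**Working it through.** **The plan's own figure.** There is none for Model B. The only usable planning inputs are those of Section 3.5 for the main trial.

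**Inputs from the protocol**
- 724 patients and 5% lost to follow-up (Section 3.5).
- "The expected recurrence rate of AF is 30% for control group" (Section 3.5).
- 12 months of follow-up per participant (Section 3.1).
- Threshold P < 0.05 (Section 8).

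**Assumptions, not in the protocol**
- The 30% applies to both arms as a 12-month proportion.
- The test is two-sided.
- The log interval is normal and its effect is log-linear. The illustrative effect is HR 1.20 per SD, with 1.15 and 1.25 as a range.
- Groups are equal-sized quantile groups.

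**Step 1, events.** 724 × 0.95 × 0.30 = 206.3.

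**Step 2, information on the continuous scale.** Non-centrality = events × (ln HR)². At HR 1.20: 206.3 × 0.1823² = 6.86. One-df power is about Φ(√6.86 − 1.96) = Φ(0.66) = 74.5%.

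**Step 3, share of information kept by grouping.** For a normal covariate the share is the between-group variance (unordered test, k − 1 df) or the squared correlation with equally spaced group scores (trend test, 1 df).

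| Groups | Unordered | Trend |
|---|---|---|
| 2 | 0.637 | 0.637 |
| 3 | 0.793 | 0.793 |
| 4 | 0.861 | 0.856 |
| 5 | 0.897 | 0.888 |

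**Step 4, power.** Multiply the non-centrality by the share and refer it to the non-central chi-square. Example, tertiles at HR 1.20: 6.86 × 0.793 = 5.44, which gives 54% on 2 df and 64.5% on 1 df.

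| Analysis | HR 1.15 | HR 1.20 | HR 1.25 |
|---|---|---|---|
| Continuous, 1 df | 52% | 74.5% | 89% |
| 2 groups | 36% | 55% | 72% |
| 3 groups, unordered | 34% | 54% | 73% |
| 4 groups, unordered | 31% | 51% | 70% |
| 3 groups, trend | 43% | 64.5% | 81% |
| 4 groups, trend | 46% | 68% | 84% |
| 5 groups, trend | 47% | 69% | 86% |
| 3-knot spline, 2 df | 42% | 65% | 83% |

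At HR 1.20 the loss against the continuous term runs from about 5 points (74.5 − 69.4, trend over five groups) to about 23 points (74.5 − 51.1, four unordered groups).

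**Step 5, simulation check.** Cox score tests in 4,000 simulated trials of 688 patients (724 × 0.95), HR 1.20 per SD and about 206 events, gave 75% for the continuous term. Two, three and four unordered groups gave 55%, 55% and 51%. Trend over three, four and five groups gave 66%, 68% and 70%.

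**Step 6, sensitivity to the distribution.** Set the continuous test at 80% power. A median split then loses 19 points with a normal covariate and 12 with a uniform one. If the effect is linear on the raw scale, the median split loses 31 points with an exponential interval and 49 with a lognormal one (log-SD 1). At the other extreme, a trend test over five groups of a uniform covariate loses under 2 points. In the lognormal raw-scale case a log-interval term is itself misspecified and keeps about 58% of the information, but two to five quantile groups keep only 27% to 53%.

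**The case against.** The strongest reply is that the size of the loss is not a property of this plan. Section 8.1.3 does not exclude a trend test across ordered groups. With three groups that test matches a 2-df spline test, and with four or five it exceeds it. This stands, and it has two consequences. The loss must be given as a range under stated assumptions. The replacement test should be the 1-df continuous term, because testing on the spline would give back most of the gain.

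A reader might infer that data-derived cut-points inflate the type I error. The text does not support that. The wording most naturally refers to the distribution of the interval, which is known at ablation, and cut-points that ignore the outcome do not inflate the error rate. What remains open is the number and position of the groups, since quantiles are not specified.

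A reader might also infer that Model A makes the same mistake. It does not say that duration is categorised, so there is nothing there to correct.

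Finally, the sub-analysis is exploratory, carries no power claim or decision rule, and is not listed among the primary or secondary endpoints. That limits the weight of the point but does not remove it: the protocol does choose categories, and a better choice is available at almost no cost.

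**Conclusion.** The point holds as a minor one. Model B, as written, uses a continuous interval only through categories specific to this sample. That loses information and makes the result harder to compare with other cohorts.

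Under the base assumptions (about 206 events, normal log interval, HR 1.20 per SD, two-sided 5%), the loss is about 5 to 23 points of power, depending on the number of groups and on whether their order is used. It would be wrong to attach one fixed loss to the plan, because the protocol states none of the quantities that determine it; other plausible distributions widen the range in both directions. A true step effect located at one of the chosen cut-points would reduce the advantage of the continuous term. The primary non-inferiority conclusion is not affected.

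**What to change.** In Section 8.1.3, Model B:

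1. Base the test of association on the log-transformed interval as a single continuous term (1 df) in a Cox model for the primary efficacy endpoint.
2. Use a restricted cubic spline with three knots at prespecified percentiles only to check and display the shape.
3. Keep categories for display, by a quantile rule (number of groups and percentiles) fixed before outcomes are seen.
4. For comparability of the two time definitions, analyse documented AF duration in Model A on the same continuous scale. This aligns the models and does not correct an error in Model A.

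The cost is a few sentences, with no new data, visits or patients. The drawback is that a hazard ratio per unit of log time is slightly harder to present than group rates; the displayed categories cover that need.
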